To evaluate the concordance of TFV-DP and FTC-TP in DBS with adherence measured by DOT Diary. Validation of DOT will focus on concordance between aDOT-based assessments of PrEP adherence by the AiCure device with four DBS measurements. *First*, we will use a pharmacokinetic (PK) model with parameters estimated in the DOT-DBS Study (NCT02022657) to calculate the expected TFV-DP levels when each DBS is obtained, based on the aDOT-confirmed pattern of pill-taking over the previous 6 weeks, as assessed using aDOT-confirmed results. In sensitivity analyses, we will include self-reported pill-taking. We will then estimate the correlation between these predictions and observed TFV-DP levels based on DBS, and scatterplot the two measures against each other, with a Lowess smooth. As an additional measure of concordance, we will estimate the proportion of 90% prediction intervals obtained from the PK model that include the measured DBS TFV-DP levels. **Second**, we will also use aDOT-confirmed aDOT records of pill-taking over the previous 4 and 8 weeks to estimate the average number of PrEP doses per week taken by each participant, then estimate concordance of aDOT- and DBS-based indicators for protective dosing of 4-7 doses/week, with 95% confidence intervals. The DBS indicator will be defined by TFV-DP levels ≥700 fmol/punch. We will also assess concordance of aDOT- and DBSbased measures of <2, 2-3, and 4-7 doses per week, using the Kappa statistic. Third, we will estimate concordance between an aDOT-based indicator for any PrEP use over the previous 48 hours with an indicator for detection of FTC-TP in DBS, again with 95% confidence intervals. Margins of sampling error (MSEs). The expected sample of 240 DBS (an average of 3.59 from each of 67 participants, accounting for cumulative 20% loss to follow-up over 24 weeks) will allow us to estimate the concordance of paired binary measures within MSEs of 6.3-8.4 percentage points, depending on the sample concordance. MSEs for concordance of DOT results with detection of FTC-TP will be similar.

To assess the acceptability and ease of use of DOT Diary over a 24 week period.

Acceptability and ease of use will be measured using the System Usability Scale (SUS) and

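### The PK comparison in objective 2a has no statistic that estimates how far, and in which direction, the app mis-records doses on average

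*SAP*

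**What the plan says.** Concordance with dried-blood-spot (DBS) drug levels is the second of three primary objectives (Protocol 2.1 and 6.2.1; SAP, Primary Objectives). The first of its three validation steps uses a "pharmacokinetic (PK) model with parameters estimated in the DOT-DBS Study" to predict TFV-DP at each sample, "based on the aDOT-confirmed pattern of pill-taking over the previous 6 weeks". The predicted and observed levels are then compared in three ways:

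- a correlation: "We will then estimate the correlation between these predictions and observed TFV-DP levels based on DBS" (type and scale not stated, no interval);
- a graph: "scatterplot the two measures against each other, with a Lowess smooth";
- coverage, where the plan is to "estimate the proportion of 90% prediction intervals obtained from the PK model that include the measured DBS TFV-DP levels".

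The SAP adds, for unrecorded doses: "In sensitivity analyses, we will include self-reported pill-taking". The other two steps are categorical. One will "estimate concordance of aDOT- and DBS-based indicators for protective dosing of 4-7 doses/week, with 95% confidence intervals" and give a kappa over three dosing categories. The other compares app-recorded use in the past 48 hours with FTC-TP detection. Neither document plans a mean difference or ratio, limits of agreement, a calibration intercept or slope, or a split of disagreements by direction. No acceptance threshold is stated for any measure.

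**The concern.** Correlation measures association, not agreement. If every prediction is too low by the same factor, Pearson's r is unchanged on the raw or the log scale. An app that misses a steady share of swallowed doses produces nearly that pattern. Prediction-interval coverage does respond to bias, but equally to intervals that are too narrow or too wide, and it does not say whether predictions run high or low.

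Direction matters because the protocol itself describes both kinds of error. Sections 5.2 and 6.1 describe flagging of feigned doses, which if missed lead to over-recording. Section 5.6.3 covers prolonged non-use and overrides, which can go with doses taken off camera and hence under-recording. Section 1.0 motivates the app by the need to track ingestion accurately so that PrEP efficacy can be estimated without bias, and this pilot prepares for a larger trial. An estimate of the average recording error is the natural result of such a validation, and it is not planned.

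**Working it through.** **1. The plan's own figures.** If retention falls geometrically to 80% over the four visits, samples per participant are 1 + 0.8^(1/3) + 0.8^(2/3) + 0.8 = 1 + 0.928 + 0.862 + 0.800 = 3.59. Times 67 this is 240.5, the stated 240. With the plan's ICC of 0.69, the design effect is 1 + 2.59 × 0.69 = 2.787, so effective n = 240.5/2.787 ≈ 86. The margin 1.96√(p(1−p)/86) is 6.3 points at p = 0.90 and 8.4 at p = 0.80. The stated 6.3-8.4 points are reproduced.

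**2. Assumptions not in the documents.** TFV-DP is proportional to dose. The log-scale SD of observed around predicted is 0.3, 0.4 or 0.5. The 0.69 ICC, given for the binary TFV-DP outcome, carries over to this comparison.

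**3. Correlation.** In simulation (PK coefficient of variation 40%), an app missing 0/10/20/30% of taken doses gives r = 0.63/0.62/0.61/0.59. The geometric mean ratio of observed to predicted moves 1.00/1.11/1.26/1.44. Crediting 20% or 40% of missed doses gives r = 0.62 or 0.60 and a ratio of 0.87 or 0.79.

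**4. Coverage.** For a constant bias, coverage = Φ(1.645 − d) − Φ(−1.645 − d), with d = ln(1/0.8)/SD = 0.223/SD at 80% recording. The chance that coverage differs significantly from 90% depends on the standard error used:

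| Log-SD | d | Coverage | (a) SE at the reduced coverage, n = 86 | (b) SE at 90%, n = 86 | (c) as (b), ICC 0.69 on the residuals |
|---|---|---|---|---|---|
| 0.3 | 0.74 | 81% | 58% | 75% | 85% |
| 0.4 | 0.56 | 85% | 27% | 39% | 48% |
| 0.5 | 0.45 | 87% | 15% | 21% | 26% |

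In (b) and (c) the critical value is set from the SE at 90% coverage. In (c) the inside/outside indicator has a lower ICC than the residuals (about 0.37-0.42 under the bias), so effective n rises to about 115-123. Using the still lower ICC at 90% coverage for the critical value gives 87/52/28%. At SD 0.2, d = 1.12 and coverage is 70%.

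**5. Mean log ratio.** The 95% half-width is 1.96 × SD/√86 = 0.063, 0.084 or 0.106, about 6%, 8% or 11%, against a shift of 0.223. Power is 98% or more in all three cases, taking the PK parameters as known. In units of the prediction SD, 80% power needs a bias of about 0.77 by coverage and 2.80/√86 = 0.30 by the mean log ratio. At week 24, with about 54 participants, the half-width is 1.96 × SD/√54 = 0.08, 0.11 or 0.13.

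**6. Over-recording is not a constant factor.** If true adherence is a and a share f of missed doses is credited, recorded/true = 1 + f(1 − a)/a. With f = 0.2 this is 1.02 at a = 0.9, 1.09 at 0.7, 1.20 at 0.5 and 1.47 at 0.3. The error is concentrated in poor adherers, so a single average ratio does not describe it fully.

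**The case against.** The strongest reply is that the plan looks at more than r and coverage. The Lowess scatterplot can show the direction and shape of a departure, and it would bend or tilt under over-recording. That stands, but the plan specifies no identity line, estimate or interval, so the reading is by eye.

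The categorical measures also react to large errors. In the step 3 simulation, agreement at 4-7 doses per week falls from 0.79 to 0.66 when 30% of doses are missed. At 10% missed it is 0.78, and neither overall agreement nor kappa gives a direction. The self-report analysis bears on under-recording but is not paired with any bias estimate and does not address feigned doses. Human review of flagged events, and exit interviews that ask whether the app data are accurate, help to find individual problems. They do not measure average error.

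Coverage is not always weak. At log-SD 0.3 its power may reach about 85%, and at 0.2 the error is obvious. Any statement that it is insensitive depends on a PK spread that the documents do not give.

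Finally, the precision of the ratio is for the ratio, not for app error alone. The PK parameters come from another study, and their uncertainty is outside the 6-11% half-width. A calibration shift in that model would look the same as app bias. This stands, though correlation and coverage share the dependence on the borrowed model.

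**Conclusion.** The concern holds in a limited form. On the continuous scale, no planned statistic estimates systematic over- or under-recording, so a moderate average error would be left unquantified within a primary objective. For an app recording 80% of doses, coverage would move from 90% to about 81-87% and be detected with anything from 15% to 85% power. This range rests on an assumed log-SD of 0.3-0.5, the carried-over ICC and the choice of standard error. A mean log ratio from the same samples would place the error within about 6-11% and give its sign, conditional on the PK model.

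A reader might infer that a biased app could pass validation. The documents do not support that: no measure has an acceptance rule, so nothing is passed or failed. Nor do they support the inference that bias would go unseen altogether. Large errors would lower coverage and categorical agreement, and the plot may show them. The randomised comparison under objective 1 uses measured TFV-DP and is unaffected.

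**What to change.** In objective 2a (SAP, Primary Objectives; Protocol 6.2.1):

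- Pre-specify the mean of log(observed/predicted) TFV-DP, reported as a geometric mean ratio with a 95% confidence interval clustered by participant, overall and by visit.
- Add the calibration slope of log observed on log predicted, because over-recording error varies with true adherence. Random error in the predictions also pulls this slope down, so it should be read with the plot.
- Draw an identity line on the planned scatterplot.
- Keep the correlation and interval coverage as supporting summaries.

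The cost is SAP wording and a few summaries of values already computed, with no new samples or visits. The downside should be stated in the SAP. A ratio away from 1 combines app recording error with misfit of the borrowed PK model, including any effect of the 6-week dose window, and cannot separate them. The interval also leaves out uncertainty in the external PK parameters.

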5.2 DOT Diary app

DOT Diary is a smartphone app designed to track participant adherence to oral PrEP use and sexual behaviors on a day-by-day basis. DOT Diary is built upon AiCure's HIPAA-compliant platform which uses artificial intelligence (computer vision and machine learning) to visually monitor adherence to treatment. Computer vision and neural networks confirm that the correct participant is presenting the correct medication and ingesting the medication. Real-time data (dosing data and patient reported outcomes) are transmitted to a centralized, cloud-based, system for analysis and

intervention. Data are presented to study personnel on a browser-based dashboard. Study personnel may switch on automated notifications (notifications are based on adherence thresholds). Study personnel receive weekly updates regarding participants. In addition to dosing data, the platform will automatically flag behavioral events for further review that may be indicative of a participant intentionally not taking the medication, or 'feigning' adherence. If deceptive behavior is confirmed by human review, study personnel are notified. On the participant side, the aDOT application is downloaded onto a smartphone and works via the front-facing camera. Dosing data are encrypted and stored, then transmitted to centralized servers; all protected health information (PHI) is encrypted and withheld from view on the dashboard.

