6.0 Data management and analysis

6.1 Data management

CASI data will be collected online using Qualtrics and stored in password-protected databases. The aDOT app will require a unique log-in and password and secure connections will be utilized as a way to protect confidentiality. Participants will be assured that the information they provide will be managed with the highest standards of confidentiality. All study staff will be trained in Good Clinical Practice (GCP) and will have received additional training about maintaining confidentiality.

The AiCure smartphone app makes a real-time determination of whether the participant has properly administered their medication, providing reminders and encouraging following proper procedures to ensure medication ingestion as prescribed. Study participants will receive a medication reminder at a time within a predefined window. This notification reminds participants to take their medication dose while using the AiCure smartphone app. Participants will follow a series of prescribed steps in front of the front-facing webcam to visually confirm their ingestion of the medication. The application on the smartphone will make an automated determination of whether the patient has properly taken their medication at the prescribed time. There is no need for study personnel to review the administration, nor would study personnel need to be available at the time the participant takes their medication. The amount of guidance that the device provides to the participant is automatically reduced as the participant becomes more proficient at using the application.

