DOT Diary Longitudinal Pilot Statistical Analysis Plan

NCT03771638

PI: [name] Date: April 5, 2019

Statistical Analysis Plan

Primary Objectives

To assess the effect of DOT Diary on PrEP adherence as measured by TFV-DP in DBS among young MSM initiating PrEP. We will use GEE logistic models to estimate the average effect of assignment to DOT Diary on repeated TFV-DP levels ≥700 fmol/punch, which are consistent with taking 4-7 PrEP doses per week. In exploratory analyses, we will examine whether the between-group difference increases over time. We will also use analogous GEE linear models to estimate the effects of D2 on log-transformed TFV-DP levels, as well as GEE proportional odds models for an ordinal outcome defined as TFV-DP levels consistent with <2, 2-3, and 4-7 doses per week, using cut-points determined by pharmacokinetic benchmarks established through directly-observed dosing.²⁸ To help with interpretation of these results, retention in the study will at each 6-week visit will be reported. Minimum detectable effects (MDEs). We used data from the EPIC study to estimate the baseline level and intraclass correlation (ICC) of the repeated binary measures of DBS TFV-DP levels ≥700 fmol/punch as 60% and 0.69 respectively, and retention of 80% of participants at 24 weeks. Under these assumptions, we will have 80% power in 2-sided tests with a type-I error rate of 5% to detect average between-group differences in adherence of 23 percentage points.

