Client Satisfaction Questionnaire (CSQ-8) adapted for use in the DOT Diary Longitudinal pilot.²⁹ Average values of our measures of acceptability and ease of use will be estimated with 95% confidence intervals. *MSEs.* The estimated sample of 54 participants providing end of study data will allow us to estimate mean SUS and CSQ-8 scores within MSEs of 0.27 standard deviations (SDs).

Secondary Objectives

To assess PrEP coverage of sexual acts (prevention-effectiveness adherence) as measured by DOT Diary. We will estimate the probability of coverage of condomless receptive sexual acts in each period, with sexual acts treated as trials, and coverage as success. Confidence intervals will be obtained using GEE binomial models, with robust standard errors will be used to account for within-subject correlation as well as over-dispersion of the binomial outcome. *MSEs.* We also used EPIC data to estimate the average number of condomless receptive sexual acts per participant as ~7. Under this assumption, we will be able to estimate coverage probabilities within MSEs of 4-10 percentage points, depending on coverage levels and the ICC of coverage across episodes.

To evaluate the daily use of the DOT and diary components of DOT Diary through 24 weeks of follow-up. We will estimate the average use of DOT and the diary, as proportions of days and weeks on study, respectively. In the primary ITT analysis, participants will be included in the denominator through 24 weeks, regardless of dropout. In a per-protocol analysis, participants will be omitted from the denominator after dropout. *MSEs.* Proportions will be estimated within MSEs of 7-12 percentage points, depending on the sample proportions.

Subgroup analyses. Four pre-specified subgroup analyses will conducted in which interaction terms will be added to the primary GEE logistic models for protective DBS levels, to assess modification of treatment effects by 1. site; 2. age (categorized as <25 and 25+); 3. race/ethnicity, categorized as African American or Latinx vs White or other; and 4. prior PrEP use. Within-subgroup effect estimates will be presented only if the corresponding omnibus test for treatment-subgroup interaction is statistically significant at P<0.15, and results will be presented as exploratory.

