Exploratory analyses of treatment effect mechanism. Standard per-protocol analyses focused on treatment effects among participants who are adherent to blinded placebo-controlled treatment are not feasible in a context where use of the app is directly tied to pill counts and DBS results. For the same reason, the design also precludes standard mediation analysis assessing treatment effects on the mediator as well as effects on the primary outcome before and after adjustment for the mediator. To better understand how any effect occurs, we will explore associations between aDOT-confirmed pill counts and time spent using the app overall, as well as time spent with the sexual diary, within the intervention arm. In addition, we will assess the relationships among sexual risk, as measured via the diary, pill counts, and DBS results.

Qualitative Data analysis. Recordings of the in-depth interviews (IDIs) will be analyzed using DeDoose software for qualitative analysis. The analysis team will include members at both San Francisco and Atlanta study site, as well as a representative from AiCure. Interviewers will complete a debrief report promptly following each interview to capture results relevant to the study objectives. Debrief reports will also include an assessment of

whether the interview merits additional in-depth analysis. Debriefing reports have been shown to be of sufficiently high quality to use as a primary source.³⁰ Debrief reports and selected transcripts will be reviewed for emergent themes and results relevant to the study objectives. Team members will create summary reports based on this analysis for use in providing feedback and suggestions in achieving study goals, and to contribute to manuscript development. Debrief reports will be reviewed promptly in order to provide feedback and suggestions for subsequent interviews. The first two audio recorded interviews and resulting debrief report at each site will be reviewed by a member of the team at the other site in order to assure uniformity in interview approaches and information included in debrief reports.

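### Relating camera-confirmed pill counts to overall app time builds in a shared component, so an association (usually positive, size unknown) can arise even if the app changes no pill-taking

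*SAP*

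**What the plan says.** The SAP paragraph on exploratory analyses of treatment effect mechanism rules out standard per-protocol and mediation analyses because "use of the app is directly tied to pill counts and DBS results". It then turns to what can be done within the intervention arm: "we will explore associations between aDOT-confirmed pill counts and time spent using the app overall", with time in the sexual diary as a separate second measure. It adds that "we will assess the relationships among sexual risk, as measured via the diary, pill counts, and DBS results". It does not say whether app time is a total, a daily figure or a per-session average, and it does not take dosing sessions out of the overall figure.

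Protocol 6.1 describes how a dose becomes confirmed: "Participants will follow a series of prescribed steps in front of the front-facing webcam to visually confirm their ingestion of the medication". The same section notes that "The amount of guidance that the device provides to the participant is automatically reduced as the participant becomes more proficient at using the application". Protocol 5.2 says that "the platform will automatically flag behavioral events for further review that may be indicative of a participant intentionally not taking the medication", and Protocol 5.6.3 provides for staff contact after prolonged non-use or repeated overrides.

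The sample-size text assumes "retention of 80% of participants at 24 weeks". For the daily-use objective the SAP says how dropouts enter the denominator: they count through week 24 in the main analysis, and "In a per-protocol analysis, participants will be omitted from the denominator after dropout". The mechanism paragraph has no such rule.

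**The concern.** A confirmed dose cannot exist without app time. If time is summed over follow-up or averaged per day, the pill count is partly contained in the variable it is set against. The association then cannot separate an app that helps people take pills from the plain fact that dosing on camera takes time. The SAP names this tie as a reason to drop two other analyses but attaches no caveat to this one.

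A second link is time on study. Someone who leaves early accrues fewer confirmed pills, less app time and less diary time.

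At stake is a misreading that could influence how the app is refined before a larger trial, which Protocol section 1.0 gives as a purpose of the pilot. No planned analysis sets app or diary time against DBS, the adherence measure that the app does not record.

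**Working it through.** The plan gives no figure for this analysis, so there is none to reproduce. The check is algebra followed by simulation.

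**Algebra.** For one participant let C be confirmed doses, s the mean time per confirmed session, U the time in unconfirmed sessions and O all other app time. Overall time is T = C·s + U + O, so

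Cov(C, T) = Cov(C, C·s) + Cov(C, U) + Cov(C, O).

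- The first term is positive unless s falls about as fast as C rises. Reduced guidance with practice weakens it.
- The second tends to be negative, because unconfirmed sessions fall on days without a confirmed dose.
- The third is zero if other use is unrelated to dosing and everyone has equal follow-up. On totals with dropout it is positive.

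If time is expressed per confirmed dose, the count no longer accumulates in it. In a simulation that correlation was about -0.4, so the point is limited to total or per-day time.

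**Simulation with no app effect.** From the documents: 67 intervention participants (Protocol 5.3), 168 days, and 0% or 20% dropout. Everything else is assumed:

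- Pill probability is Beta(4, 1.5). App-use probability is independent of it: Beta(1.5, 1), Beta(3, 1) or Beta(5, 1.2).
- Sessions are fixed at 1 minute or shorten with practice, times a person factor with log-SD 0, 0.4 or 0.6.
- Unconfirmed sessions occur on 0% or 30% of days without a confirmed dose.
- Other time is scaled to give the dosing share shown.

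There were 2,000 runs per setting. Results for total time without dropout:

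| Dosing share of app time | Mean r, confirmed pills vs app time | Runs with P<0.05 |
|---|---|---|
| 90% | 0.17 to 0.98 | 27-100% |
| 75% | 0.15 to 0.84 | 23-100% |
| 50% | 0.09 to 0.46 | 12-97% |
| 25% | 0.03 to 0.17 | 6-30% |
| 10% | 0.01 to 0.06 | 4-8% |

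Values above 0.9 need identical session lengths. At log-SD 0.4 the range is 0.25-0.74 for a 90% share and 0.20-0.67 for 75%. A separate simulation assumed about 60 seconds per dose and non-dosing time of 15 to 240 seconds per day. It gave 0.60 down to 0.05 with constant time per dose, and 0.36 down to 0.03 if time per dose falls by up to half.

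**When the sign changes.** At a 75% share and log-SD 0.4, unconfirmed sessions on 60% of the remaining days and 1.5 times as long give r of about 0.04. On 90% of those days and twice as long, r is about -0.21. If poorer app users have longer sessions (log-slope -0.3 to -0.4 per SD of app-use probability), r is about -0.02 to -0.18.

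**Time on study.** With 20% dropout, total diary time has r of 0.06-0.10 with confirmed pills under no effect (P<0.05 in 7-13%). Dividing both by days on study returns it to about 0.00 (4-6%). The same division leaves overall app time at 0.14-0.84 for a 75% share, so it removes the second link but not the first.

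**Changing only the outcome.** With TFV-DP in DBS as outcome and overall app time as exposure (75% share, log-SD 0.4), r is still 0.17-0.24 under no effect, because dosing sessions track real pills. The exposure has to change too.

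**Precision of a DBS analysis.** Constant attrition between visits to 80% gives 1 + 0.928 + 0.862 + 0.80 = 3.59 DBS per person, and 67 × 3.59 ≈ 240. Both match the SAP. With the stated ICC of 0.69 (given for the binary indicator, assumed here for both outcomes), the effective number for a person-level exposure is 240 / (1 + 2.59 × 0.69) ≈ 86. The correlation detectable with 80% power is tanh(2.80 / √83) ≈ 0.30, or 0.27-0.31 for ICC 0.5-0.8.

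**The case against.** The SAP labels the analysis exploratory, states the tie itself, and plans no test, threshold or causal claim. Diary time, which contains no dosing steps, is already a separate planned measure, and app-recorded doses are compared with DBS under the second primary objective. All of this is true and limits the weight of the point. None of it tells a reader that the overall-time association is partly built in.

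A reader might infer that a positive association is guaranteed. The documents do not support that. They give no durations, do not fix the time variable, and foresee overrides and feigned doses. The shared component is certain on total or per-day time; the net sign and size are not, and at a small dosing share the effect is negligible.

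The strongest objection concerns the remedy. Relating diary time to DBS removes the built-in link but not confounding, since engaged people may both use the diary and take their pills. With no app effect and latent correlations between diary use and pill-taking of 0, 0.2, 0.3 and 0.5, a GEE of log TFV-DP on log(1 + diary time) with bias-reduced standard errors gave P<0.05 in about 4%, 20%, 47% and 85% of 200 runs. This stands, and the added model must be presented accordingly.

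**Conclusion.** The point holds as a minor one. On total or per-day time, the overall-app-time association contains a component created by the dosing sessions themselves and cannot be read as evidence of how the app works. Totals carry a further, smaller link through time on study. The size depends mainly on the dosing share of app time, the spread of session lengths and the frequency of unconfirmed sessions, none of which the documents give. All simulated figures are therefore illustrations under stated assumptions.

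Two further readings go too far. The randomized comparison of TFV-DP between arms does not use app time and is unaffected. The diary-time association does not share the dosing link; as a total it shares only time on study, and like any such association it is open to confounding by engagement.

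**What to change.** 1. Define app time in the SAP, and express confirmed counts and all times per day on study.
2. Keep the association with overall app time, but report it only as a description of app use, with the dosing share of time if it is logged. For the mechanism question use diary time as the exposure, and non-dosing app time if the logs separate it.
3. As an additional exploratory analysis within the intervention arm, relate that exposure in the 6 weeks before each DBS to TFV-DP (log level and the 700 fmol/punch indicator) by GEE. Use log(1 + time) and a small-sample-corrected robust standard error such as Mancl-DeRouen. In simulations without confounding this gave P<0.05 in 4-6% (log level) and 4-5% (indicator) of runs, against 8-11% and 6-7% with raw time and the plain robust error.
4. State that step 3 removes the built-in link but not confounding by engagement or by staff outreach after non-use, so it is an association and not by itself evidence of mechanism.

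The cost is SAP wording and a little programming. DBS is already collected at weeks 6, 12, 18 and 24 (Protocol 8.2), and the raw platform data are to be supplied at study end (Protocol 6.1). The downsides are low precision (detectable r about 0.30), no information on the on-camera dosing component, and dependence on separate logging for non-dosing time, which the documents do not confirm. If the added model is declined, steps 1 and 2 still prevent the misreading.
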